5.4 Attribution of Adverse Events

Investigators are required to assess whether there is a reasonable possibility that afatinib and/or MK-3475 caused or contributed to the adverse event. The following general guidance may be used.

- Definite – The AE is *clearly related* to the study treatment.
- Probable – The AE is *likely related* to the study treatment.
- Possible – The AE *may be related* to the study treatment.
- Unlikely – The AE is *doubtfully related* to the study treatment.
- Unrelated – The AE is *clearly NOT related* to the study treatment.

If an adverse event is attributable (either definite, probable or possible) to MK-3475 and/or afatinib that requires the drug be held the other drug may be continued if it the adverse event is not attributable to that drug (either unlikely or unrelated) with approval of the treating physician and primary investigator. Exceptions include pneumonitis and grade 2 and above enterocolitis (as defined in this protocol) where both MK-3475 and afatinib must be held.

5.5 Concomitant Medications/Vaccinations (allowed & prohibited)

Medications or vaccinations specifically prohibited in the exclusion criteria are not allowed during the ongoing trial. If there is a clinical indication for one of these or other medications or vaccinations specifically prohibited during the trial, discontinuation from trial therapy or vaccination may be required. The investigator should discuss any questions regarding this with the Merck and/or Boehringer Ingelheim. The final decision on any supportive therapy or vaccination rests with the investigator and/or the subject's primary physician.

5.5.1 Acceptable Concomitant Medications

All treatments that the investigator considers necessary for a subject's welfare may be administered at the discretion of the investigator in keeping with the community standards of medical care.

All concomitant medications received within 28 days before the first dose of trial treatment and 30 days after the last dose of trial treatment should be recorded. Concomitant medications administered after 30 days after the last dose of trial treatment should be recorded for SAEs and Event(s) of clinical interest. ECIs guidance document attached within the appendices.

5.5.2 Prohibited Concomitant Medications

Subjects are prohibited from receiving the following therapies during the Screening and Treatment Phase (including retreatment for post-complete response relapse) of this trial:

- Antineoplastic systemic chemotherapy or biological therapy
- Immunotherapy not specified in this protocol
- Chemotherapy not specified in this protocol
- Investigational agents other than MK-3475 and afatinib
- Radiation therapy
 - Note: Radiation therapy to a symptomatic solitary lesion or to the brain may be allowed at the Investigator's discretion.
- Live vaccines within 30 days prior to the first dose of trial treatment and while participating in the trial. Examples of live vaccines include, but are not limited to, the following: measles, mumps, rubella, varicella/zoster, yellow fever, rabies, BCG, and typhoid vaccine.
- Systemic glucocorticoids for any purpose other than to modulate symptoms from an event of clinical interest of suspected immunologic etiology. The use of physiologic doses of corticosteroids may be approved after consultation with the Sponsor-Investigator.
- Strong inducers or inhibitors of P-glycoprotein that are known to interact with afatinib including, but not limited to: ritonavir, cyclosporine A, ketoconazole, itraconazole, erythromycin, verapamil, quinidine, tacrolimus, nelfinavir, saquinavir, and amiodarone. Because the lists of these agents are constantly changing, it is important to regularly consult a frequently-updated list such as <http://medicine.iupui.edu/clinpharm/ddis/table.aspx>; medical reference texts such as the Physicians' Desk Reference may also provide this information.

Subjects who, in the assessment by the investigator, require the use of any of the aforementioned treatments for clinical management should be removed from the trial. Subjects may receive other medications that the investigator deems to be medically necessary.

The Exclusion Criteria describes other medications which are prohibited in this trial. There are no prohibited therapies during the Post-Treatment Follow-up Phase.

In case of major surgery (as judged by the investigator), it is recommended to stop treatment with afatinib around one week prior to the surgery, and to restart treatment after complete wound healing. If afatinib is interrupted for more than 14 days, the decision to continue will be made by the Sponsor-Investigator.

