22. The presence of poorly controlled gastrointestinal disorders that could affect the absorption of the afatinib (e.g. Crohn's disease, ulcerative colitis, chronic diarrhea,

malabsorption).

23. Receiving drugs known to be strong inducers or inhibitors of P-glycoprotein that are known to interact with afatinib including, but not limited to: ritonavir, cyclosporine A, ketoconazole, itraconazole, erythromycin, verapamil, quinidine, tacrolimus, nelfinavir, saquinavir, and amiodarone. Because the lists of these agents are constantly changing, it is important to regularly consult a frequently-updated list such as <http://medicine.iupui.edu/clinpharm/ddis/table.aspx>; medical reference texts such as the Physicians' Desk Reference may also provide this information. As part of the enrollment/informed consent procedures, the patient will be counseled on the risk of interactions with other agents, and what to do if new medications need to be prescribed or if the patient is considering a new over-the-counter medicine or herbal product. The subject must stop the strong inducer or inhibitor of P-glycoprotein 7 days before or 5 half lives before study drug administration (whichever timepoint is longer).
24. Major surgery within 4 weeks before starting study treatment or scheduled for surgery during the projected course of the study.
25. Radiotherapy within 4 weeks prior to enrollment, except as follows:
 - i.) Palliative radiation to target organs other than chest may be allowed up to 2 weeks prior to enrollment, and
 - ii.) Single dose palliative treatment for symptomatic metastasis outside above allowance to be discussed with sponsor-investigator prior to enrolling.
26. Meningeal carcinomatosis.
27. Prior participation in an afatinib clinical study, even if not assigned to afatinib treatment.
28. Any history of or concomitant condition that, in the opinion of the Investigator, would compromise the patient's ability to comply with the study or interfere with the evaluation of the efficacy and safety of the test drug.

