2. In general, the window for each visit is \pm 3 days unless otherwise specified.
3. For women of reproductive potential, a urine or serum pregnancy test will be performed within 72 hours prior to first dose of trial treatment. If urine pregnancy results cannot be confirmed as negative, a serum pregnancy test, performed by the local study site laboratory, will be required. Pregnancy tests (serum and/or urine tests) should be repeated if required by local guidelines.
4. Coagulation factors (PT/INR and aPTT) should be monitored closely throughout the trial for any subject receiving anticoagulant therapy.
5. Laboratory tests for screening are to be performed within 10 days prior to the first dose of trial treatment.
6. After Cycle 1, lab samples can be collected up to 72 hours prior to the scheduled time point. Laboratory results must be known and acceptable prior to dosing.
7. The initial tumor imaging will be performed within 30 days prior to the first dose of trial treatment. Scans performed as part of routine clinical management are acceptable for use as the screening scan if they are of diagnostic quality and performed within 30 days prior to the first dose of trial treatment. On-study imaging will be performed every 6 weeks (42 -7 days) after the first dose of trial treatment or more frequently if clinically indicated. The timing for imaging studies should follow calendar days and should not be adjusted for delays in cycle starts or extension of MK-3475/afatinib cycle frequencies. The same imaging technique should be used in a subject throughout the trial. CT including the chest, abdomen and pelvis or PET-CT is required for the baseline assessment.
8. Provide documentation of the subject's tumor EGFR mutation from a CLIA certified laboratory.
9. MK-3475 can be administered for up to 2 years. For the dose de-escalation and Cohort (Arm) A (concurrent afatinib and MK-3475) both drugs will be administered as outlined in this protocol starting with cycle #1. For cohort B. MK-3475 will be initiated with cycle #1 and afatinib will commence in combination with MK-3475 starting with cycle #3.
10. Tumor biopsy for immune and EGFR biomarker analysis will be performed prior to Cycle 1 of treatment either on archival tissue or fresh biopsy (within 60 days). Repeat biopsy will be performed prior to initiation of cycle 3 (42 days (-7 days))

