Evaluable Non-Target Disease Response. Patients who have lesions present at baseline that are evaluable but do not meet the definitions of measurable disease, have received at least one cycle of therapy, and have had their disease re-evaluated will be considered evaluable for non-target disease. The response assessment is based on the presence, absence, or unequivocal progression of the lesions.

Disease Parameters

Measurable disease. Measurable lesions are defined as those that can be accurately measured in at least one dimension (longest diameter to be recorded) as ≥ 20 mm by chest x-ray or as ≥ 10 mm with CT scan, MRI, or calipers by clinical exam. All tumor measurements must be recorded in millimeters (or decimal fractions of centimeters).

Note: Tumor lesions that are situated in a previously irradiated area are measurable if there is evidence of growth post-radiation such as increase in size on CT or increase in FDG avidity on PET.

Malignant lymph nodes. To be considered pathologically enlarged and measurable, a lymph node must be ≥ 15 mm in short axis when assessed by CT scan (CT scan slice thickness recommended to be no greater than 5 mm). At baseline and in follow-up, only the short axis will be measured and followed.

Non-measurable disease. All other lesions (or sites of disease), including small lesions (longest diameter <10 mm or pathological lymph nodes with ≥ 10 to <15 mm short axis), are considered non-measurable disease. Bone lesions, leptomeningeal disease, ascites, pleural/pericardial effusions, lymphangitis cutis/pulmonitis, inflammatory breast disease, and abdominal masses (not followed by CT or MRI), are considered as non-measurable.

Note: Cystic lesions that meet the criteria for radiographically defined simple cysts should not be considered as malignant lesions (neither measurable nor non- measurable) since they are, by definition, simple cysts.

‘Cystic lesions’ thought to represent cystic metastases can be considered as measurable lesions, if they meet the definition of measurability described above. However, if non-cystic lesions are present in the same patient, these are preferred for selection as target lesions.

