Target lesions. All measurable lesions up to a maximum of 2 lesions per organ and 5 lesions in total, representative of all involved organs, should be identified as **target lesions** and recorded and measured at baseline. Target lesions should be selected on the basis of their size (lesions with the longest diameter), be representative of all involved organs, but in addition should be those that lend themselves to reproducible repeated measurements. It may be the case that, on occasion, the largest lesion does not lend itself to reproducible measurement in which circumstance the next largest lesion that can be measured reproducibly should be selected. A sum of the diameters (longest for non-nodal lesions, short axis for nodal lesions) for all target lesions will be calculated and reported as the baseline sum diameters. If lymph nodes are to be included in the sum, then only the short axis is added into the sum. The baseline sum diameters will be used as reference to further characterize any objective tumor regression in the measurable dimension of the disease.

Non-target lesions. All other lesions (or sites of disease) including any measurable lesions over and above the 5 target lesions should be identified as **non-target lesions** and should also be recorded at baseline. Measurements of these lesions are not required, but the presence, absence, or in rare cases unequivocal progression of each should be noted throughout follow-up.

Response Criteria

Evaluation of Target Lesions

Complete Response (CR): Disappearance of all target lesions. Any pathological lymph nodes (whether target or non-target) must have reduction in short axis to <10 mm.

Partial Response (PR): At least a 30% decrease in the sum of the diameters of target lesions, taking as reference the baseline sum diameters.

Progressive Disease (PD): At least a 20% increase in the sum of the diameters of target lesions, taking as reference the smallest sum on study (this includes the baseline sum if that is the smallest on study). In addition to the relative increase of 20%, the sum must also demonstrate an absolute increase of at least 5 mm. (Note: the appearance of one or more new lesions is also considered progressions).

Stable Disease (SD): Neither sufficient shrinkage to qualify for PR nor sufficient increase to qualify for PD, taking as reference the smallest sum diameters while on study.

Evaluation of Non-Target Lesions

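### The response rule has no exception for a target lesion irradiated after the baseline scan, so radiation shrinkage can, under limited conditions, be scored as a partial response

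*Combined protocol and SAP*

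**What the plan says.** **Radiotherapy on study.** Section 5.5.2 lists radiation among the therapies prohibited during screening and treatment, then adds a note: "Radiation therapy to a symptomatic solitary lesion or to the brain may be allowed at the Investigator's discretion". The note does not separate target from non-target lesions. After the list, the section says that subjects who "require the use of any of the aforementioned treatments for clinical management should be removed from the trial". It does not say whether radiotherapy given under the note falls within that sentence.

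**Radiotherapy before enrolment.** Exclusion 25 in section 5.1.3 has two exceptions: "Palliative radiation to target organs other than chest may be allowed up to 2 weeks prior to enrollment", and "Single dose palliative treatment for symptomatic metastasis outside above allowance to be discussed with sponsor-investigator prior to enrolling".

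**Baseline scan.** Section 6.1, footnote 7: "The initial tumor imaging will be performed within 30 days prior to the first dose of trial treatment".

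**Response.** Section 7.1.2.6 takes measurable lesions as targets, at most 2 per organ and 5 in total, and fixes their sum at baseline. Partial response is "At least a 30% decrease in the sum of the diameters of target lesions, taking as reference the baseline sum diameters". The section's one note on radiation concerns whether a lesion is measurable: "Tumor lesions that are situated in a previously irradiated area are measurable if there is evidence of growth post-radiation". Response is read by the investigator, and a confirmatory scan is asked for at least 4 weeks after a first response.

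**Use of response.** Section 8.1 calls the combination potentially worthy of further study if 3 or more of 10 Cohort A patients respond. It gives the chance of this as 7% at a true rate of 10% and 83% at a true rate of 40%. Section 8 does not mention radiotherapy.

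**The concern.** The rule of 3 in 10 is meant to measure the activity of the two drugs. A symptomatic lesion treated with radiation may shrink for that reason alone. If it is a target, its shrinkage enters the sum in the same way as shrinkage due to the drugs, and nothing in the protocol's own scoring text takes it out. With 10 patients and a bar of 3, one such patient supplies a third of the responders needed. The confirmatory scan does not help, because lasting radiation shrinkage is confirmed as readily as drug shrinkage. The person who reads response is the investigator, with whom the discretion over radiotherapy also rests, in an open-label trial.

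**Working it through.** **1. The plan's own figures.** Inputs from 8.1: n = 10, bar = 3, rates 10% and 40%. X is the number of responders.

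- P(X ≥ 3 | 10, 0.10) = 1 − 0.9^10 − 10(0.1)(0.9^9) − 45(0.1^2)(0.9^8) = 1 − 0.3487 − 0.3874 − 0.1937 = 0.0702.
- P(X ≥ 3 | 10, 0.40) = 0.8327.

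Both agree with the stated 7% and 83%.

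**2. Can the rule as written score radiation shrinkage?** Take invented targets of 40 mm and 20 mm. The first is irradiated after baseline and falls to 20 mm; the second does not change. The sum goes from 60 to 40 mm, a fall of 20/60 = 33%. This meets the partial response definition although the untreated lesion is unchanged.

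**3. When can it happen?** With the other targets stable, an irradiated lesion holding share s of the baseline sum must shrink by 0.30/s to reach a 30% fall.

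| Share of baseline sum | Shrinkage needed |
|---|---|
| 30% | 100% |
| 40% | 75% |
| 50% | 60% |
| 60% | 50% |
| 100% | 30% |

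Below a 30% share it cannot happen. The lesion must also be a target: 7.1.2.6 classes bone lesions as non-measurable, and brain radiotherapy matters only if a brain lesion is a target. Radiotherapy must come before progression, because best response is counted only up to that point.

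**4. Which timing is exposed?**

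- Irradiated before the baseline scan: covered. Without later growth the lesion is not measurable, so it cannot be a target.
- Irradiated between the baseline scan and Day 1: not clearly covered. The scan may be up to 30 days old, so it can precede permitted radiotherapy.
- Irradiated during treatment: not covered.

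**5. Illustrative size.** If one of the 10 patients is scored a responder because of radiation and the other 9 respond at 10%, the rule is passed when at least 2 of those 9 respond:

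P(X ≥ 2 | 9, 0.10) = 1 − 0.9^9 − 9(0.1)(0.9^8) = 1 − 0.3874 − 0.3874 = 0.2252.

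Alternatively, let f be the chance that a patient who does not respond to the drugs is scored a responder because of radiation. The scored rate is then p = 0.10 + 0.90f. The values of f are assumptions.

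| f (assumed) | p | P(3 or more of 10) |
|---|---|---|
| 0 | 0.100 | 7.0% |
| 1% | 0.109 | 8.7% |
| 3% | 0.127 | 12.4% |
| 5% | 0.145 | 16.7% |
| 10% | 0.190 | 29.2% |

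f is the product of how often a target is irradiated and how often that converts the score. A value of 10% needs, for example, 20% of such patients irradiated on a target and half of them converted.

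**6. Cost of the remedy.** In the worst case, one of 10 patients is barred from counting as a responder. At a true 40%, P(X ≥ 3 | 9, 0.40) = 1 − 0.6^9 − 9(0.4)(0.6^8) − 36(0.4^2)(0.6^7) = 1 − 0.0101 − 0.0605 − 0.1612 = 0.768, against 0.833.

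**The case against.** **The removal sentence may already deal with it.** On one reading, a patient who needs radiotherapy leaves the trial. On the other, the note is an exception, and reading the removal sentence to override it would leave the note with no effect. The documents do not settle this, and neither reading supplies a scoring rule. The ambiguity stands as a second item to correct.

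**Silence is not an instruction.** A reader might infer that the plan directs irradiated lesions to be counted. It does not: no sentence says so. Section 7.1.2.6 also adopts RECIST 1.1 by reference, and that paper is not part of the documents. The claim is therefore limited to the protocol's own text, which has no exception.

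**Radiotherapy before treatment.** A reader might infer that any recent palliative radiotherapy inflates response. The measurability note prevents this for lesions irradiated before the baseline scan. Only the interval from scan to Day 1 remains.

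**The conditions are narrow and the frequency unknown.** This stands. The 22.5% supposes that a radiation-driven response has already occurred, and the range for f has no support in the documents. Neither is an estimate of the trial's error rate.

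**The consequence is modest.** This also stands. The primary objective is safety, and passing the bar leads to a descriptive evaluation of response, toxicity and PFS, not to an automatic decision. A reader might infer that the comparison of Cohorts A and B is biased. Section 5.5.2 applies equally to both, and nothing in the documents shows that radiotherapy would fall more on one of them.

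**Conclusion.** The gap is real but narrow. Applied as written, 7.1.2.6 can score radiation shrinkage of a target irradiated after the baseline scan as a partial response, provided that the lesion is measurable, makes up at least 30% of the baseline sum with other targets stable, and is irradiated before progression. Section 8.1 would then count that patient toward its bar of 3. The stated 7% and 83% are correct for the rule itself. The move from 7.0% to 22.5% shows how sensitive a 10-patient rule is to one such patient; it does not show how likely that patient is. The effect reaches the secondary response endpoint and the Cohort A activity rule and no further. A delay of the PFS event through local control is conceivable, but the documents allow no size to be put on it. A short clarification is worth making because it is cheap and the decision rests on so few patients.

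**What to change.** Add to 7.1.2.6, and refer to it in 8.1:

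- A target lesion irradiated after the baseline scan, including between that scan and Day 1, cannot contribute to CR or PR.
- Best response is then the best one recorded before radiotherapy, unless the 30% decrease is met on the non-irradiated targets alone, measured against the baseline sum of those same lesions.
- A patient with no non-irradiated target left and no earlier response stays in the denominator as a non-responder.

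A PFS sensitivity analysis censoring at the last scan before radiotherapy to a target lesion is optional.

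Separately, reconcile the radiotherapy note in 5.5.2 with the removal sentence that follows the list, so that it is clear whether a patient treated under the note remains on trial. Whether and when radiotherapy is permitted is left to the sponsor.

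The cost is a few sentences, with no extra scans or patients; the date and site of any on-study radiotherapy must be available when response is scored. The downside is that a true drug responder who is irradiated may be counted as a non-responder. In the worst case for one of 10 patients, the chance of passing at a true 40% falls from 83.3% to 76.8%. If no target lesion is irradiated after the baseline scan, the stated 7% and 83% are unaffected.

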Treatment related toxicities will be managed by treatment interruptions and subsequent dose reductions of afatinib according to the schedule described in Table 6. Dose reductions will apply to individual patients only. Once the dose has been reduced, it cannot be increased later.

To prevent the development of more severe adverse events, treatment related diarrhea, nausea and vomiting or rash should be managed early and proactive as described in Section 5.6.

Products: MK-3475/Afatinib

Protocol Version 3.0
Version Date: 09/10/18

Table 6. Dose reduction scheme for Afatinib

AE Type and CTCAE Grade	Action	Dose Reduction Scheme
Events related to study drug (afatinib): 
 • Diarrhea Grade 2 persisting for 2 or more consecutive days (48 hours) despite adequate anti-diarrheal medication/hydration • Reduced renal function to \geq Grade 2 as measured by serum creatinine, proteinuria or decrease in glomerular filtration rate of more than 50% from baseline • Any drug related AE Grade ≥ 3 	
 • Pause treatment until patient has recovered to Grade ≤ 1 or baseline.¹ • Resume treatment at reduced dose according to schedule opposite. • If patient has not recovered to Grade ≤ 1 or baseline¹ within 14 days study treatment must be permanently discontinued.² 	
 • If patient was receiving 40 mg, resume treatment at a dose of 30 mg. • If patient was receiving 30 mg, resume treatment at a dose of 20 mg. • If patient was receiving 20 mg, discontinue afatinib.
Acute onset and/or unexplained worsening of pulmonary systems (dyspnea, cough, fever)	Pause afatinib while clinical assessment to exclude ILD is completed.	If ILD is ruled out as a cause of symptoms, grade symptoms and relatedness and report as AEs. If AEs are not related, resume afatinib at current dose. If AEs are drug related, follow directions in row above. If ILD is confirmed, discontinue afatinib

¹ Baseline is defined as the CTCAE Grade at the start of treatment.

² In the event that the patient is deriving obvious clinical benefit according to the investigator's judgment, further treatment with afatinib will be decided by the investigator.

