Prevention of paronychia	
 Patients should keep their hands dry and out of water if ever possible. They should avoid friction and pressure on the nail fold as well as picking or manipulating the nail. Topical application of petrolatum is recommended around the nails due to its lubricant and smoothing effect on the skin.

Table 12: Grade specific treatment recommendations of skin reactions to afatinib

Severity	Description	Specific intervention
ACNEIFORM RASH		
Mild (Grade 1)	Macular or papular eruptions or erythema without associated symptoms	Consider topical antibiotics, e.g. clindamycin 2% or topical erythromycin 1% cream or metronidazole 0.75% or topical nadifloxacin 1%; Isolated scattered lesion: cream preferred Multiple scattered areas: lotion preferred
Moderate (Grade 2)	Macular or papular eruptions with pruritus or other associated symptoms; localized desquamation or other lesions covering <30% of BSA	Topical treatment as for Grade 1 plus short term topical steroids, e.g., prednicarbate cream 0.02% plus an oral antibiotic (for at least 2 weeks) e.g. Doxycycline 100mg b.i.d. or Minocycline hydrochloride 100mg b.i.d
Severe (Grade 3)	Severe, generalized erythroderma or macular, papular or vesicular eruption; desquamation covering ≥30% of BSA; associated with pain, disfigurement, ulceration or desquamation	Topical and systemic treatment as for Grade 2. Consider referral to dermatologist Consider systemic steroids
Life threatening (Grade 4)	Generalized exfoliative, ulcerative, or bullous dermatitis	See Grade 3 Systemic steroids are recommended
EARLY AND LATE XEROTIC SKIN REACTIONS - PRURITUS		
Mild (Grade 1)	Mild or localized	Topical polidocanol cream. Consider oral antihistamines, e.g. diphenhydramine, dimethindene, cetirizine, levocetirizine, desloratadine, fexofenadine or clemastine)
Moderate (Grade 2)	Intense or widespread	See Grade 1 plus oral antihistamines; Consider topical steroids, e.g., topical hydrocortisone
Severe (Grade 3)	Intense or widespread and interfering with activities of daily living (ADL)	See Grade 2.
XEROSIS (DRY SKIN)		
Mild (Grade 1)	Asymptomatic	Soap-free shower gel and/or bath oil. Avoid alcoholic solutions and soaps. Urea- or glycerin-based moisturizer. In inflammatory lesions consider topical steroids (e.g., hydrocortisone cream)
Moderate (Grade 2)	Symptomatic, not interfering with ADL	See Grade 1. In inflammatory lesions consider topical steroids (e.g., hydrocortisone cream)

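### For severe acneiform rash attributed to afatinib, Table 12 calls for systemic steroids that Section 5.5.2 prohibits, so the same patient could be continued or removed

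*Combined protocol and SAP*

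**What the plan says.** Five places in the combined protocol and SAP bear on a patient with Grade 3 or 4 acneiform rash.

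- **Section 5.5.2** lists among the therapies prohibited during screening and treatment "Systemic glucocorticoids for any purpose other than to modulate symptoms from an event of clinical interest of suspected immunologic etiology". Physiologic doses may be approved after consultation. It then says that subjects who, in the investigator's assessment, "require the use of any of the aforementioned treatments for clinical management should be removed from the trial".
- **Section 5.5** is softer. If a prohibited medication is clinically indicated, "discontinuation from trial therapy or vaccination may be required", and "The final decision on any supportive therapy or vaccination rests with the investigator" and/or the primary physician.
- **Section 5.6.6, Table 12**, which covers skin reactions to afatinib, has sites consider systemic steroids for Grade 3 acneiform rash. At Grade 4: "Systemic steroids are recommended".
- **Section 5.1.5.3, Table 6** covers any afatinib-related event of Grade 3 or higher. Afatinib is paused until recovery, then: "Resume treatment at reduced dose according to schedule opposite". Afatinib stops if the patient was on 20 mg or, with an exception left to the investigator, has not recovered within 14 days.
- **ECI guidance document (Appendix 12.9), Table 1 and Section 3.9** make rash of Grade 3 or higher an event of clinical interest (ECI). Afatinib acneiform rash is exempt from reporting only below Grade 3. Oral steroids are recommended at Grade 3, but Section 1 of that document limits its treatment advice to events judged related to pembrolizumab.

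Sections 5.5.2 and 5.6.6 do not refer to each other on this point. Separately, the P-gp entry in Section 5.5.2 names "ritonavir, cyclosporine A, ketoconazole, itraconazole, erythromycin, verapamil, quinidine, tacrolimus, nelfinavir, saquinavir, and amiodarone" with no route of administration, while Table 12 offers "clindamycin 2% or topical erythromycin 1% cream" among its topical options for Grade 1 rash.

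**The concern.** Section 5.6.4 counts dermatologic events among the most common effects of afatinib, so the case is foreseeable. A site that follows Table 12 and Table 6 gives the steroid, pauses afatinib and continues the patient at a lower dose. A site that follows Section 5.5.2 treats the same steroid as prohibited and removes the patient. The protocol does not say which instruction takes precedence.

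The statistical interest is that removal would be caused by toxicity and would come before progression, in expansion cohorts of 10. Section 8.1 judges Cohort A on whether at least 3 of 10 respond, and compares the two cohorts on toxicity, response rate, PFS and PD-L1 change. In groups this small, whether one patient stays on treatment can affect the result.

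**Working it through.** **Step 1: apply the text to one patient.** Take a patient on both drugs with acneiform rash attributed only to afatinib.

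| Question | Grade 3 | Grade 4 |
|---|---|---|
| Table 12: systemic steroid? | Consider | Recommended |
| Section 5.5.2: allowed? | Only if an immune cause is suspected | Only if an immune cause is suspected |
| Section 5.5.2: consequence if required | Removal | Removal |
| Section 5.5: consequence | Discontinuation possible; investigator and/or primary physician decides on supportive therapy | Same |
| Table 6: consequence | Pause; resume lower on recovery if on 40 or 30 mg | Same |

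**Step 2: test the exception.** It has two conditions: the event is an ECI, and an immune cause is suspected. Grade 3 or higher rash meets the first whatever its cause. The second depends on attribution. Section 5.6.1 describes acneiform rash as an effect afatinib shares with other EGFR inhibitors, and ties its immune-event guidance to events related to pembrolizumab. If an immune cause is suspected, the steroid is allowed and there is no conflict. If the rash is attributed only to afatinib, the exception is not met. The conflict is then direct at Grade 4, and at Grade 3 it arises when the site takes up the option.

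**Step 3: reproduce the plan's figures.** Inputs from Section 8.1: n = 10, at least 3 responses to pass, true rates 10% and 40%. With X binomial(n, p), P(X ≥ 3) = 1 − Σ C(n,k) p^k (1−p)^(n−k) for k = 0, 1, 2.

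- p = 0.10: 1 − (0.3487 + 0.3874 + 0.1937) = 0.070; the plan states 7%.
- p = 0.40: 1 − (0.0060 + 0.0403 + 0.1209) = 0.833; the plan states 83%.

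**Step 4: illustrate the effect of removals.** The documents give neither a rate of steroid-treated rash nor a removal rate. Assume that m of the 10 are removed before any response is recorded, count as non-responses, and the threshold stays at 3. Then n becomes 10 − m.

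| Removed (m) | Pass at true 10% | Pass at true 40% |
|---|---|---|
| 0 | 7.0% | 83.3% |
| 1 | 5.3% | 76.8% |
| 2 | 3.8% | 68.5% |

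For m = 1 at 40%: 1 − (0.0101 + 0.0605 + 0.1612) = 0.768. A patient removed before re-evaluation might instead be classed as not evaluable under Section 7.1.2.6. If not replaced, and with the threshold unchanged, the arithmetic is the same. A response already recorded would not be lost from the count in this way, although Section 7.1.2.6 also asks for a confirmatory scan at least 4 weeks later.

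**The case against.** The strongest reply is that the text leaves room to avoid the conflict. Section 5.5 makes discontinuation only possible. Section 5.5.1 allows treatments needed for the subject's welfare. Section 5.5.2 removes only those whom the investigator judges to require the drug. Patients also receive a PD-1 antibody, so an immune cause may often be suspected. All of this is correct, and it means that following Table 12 does not by itself force removal. It does not settle the rash attributed to afatinib alone: possible discontinuation and removal are different consequences, and the steroid remains on the prohibited list.

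A reader might also infer more than the documents support:

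- **That topical erythromycin leads to removal.** It is one of four example antibiotics under a suggestion to consider, so following the table makes nobody require it. Whether the P-gp entry reaches a 1% cream is unclear.
- **That PFS, response or toxicity data are certainly lost.** Sections 2.1, 5.8 and 7.4.3.2 keep disease-status follow-up after discontinuation without progression, and Sections 5.8 and 7.4.3.1 keep adverse event follow-up. Loss is possible only because Section 5.5.2 does not say that a removed subject enters that follow-up.
- **That DLT counting or the RP2D is affected.** Maximal rash management in Section 5.3 uses neither drug. In cycle 1, a related Grade 4 rash, or Grade 3 persisting beyond 72 hours despite that management (subject to the body-surface rule for minimally symptomatic rash), counts as a DLT regardless of later handling. No effect on the RP2D is shown.
- **That sites will diverge, or relabel rash as immune-related.** Section 10.5 shows that several centers take part and the text permits different readings, but nothing documents either behavior.

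**Conclusion.** The contradiction is real but narrow. It concerns systemic steroids for Grade 3–4 acneiform rash attributed only to afatinib. There, Table 12 with Table 6 treats and, on recovery, continues the patient; Section 5.5.2 prohibits the treatment and points to removal; and Section 5.5 gives a third, discretionary consequence. ECI status does not resolve it, because the exception also needs a suspected immune cause.

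The size is illustrative. One early removal counted as a non-response takes the chance of passing Cohort A at a true 40% rate from 83% to 77%, and two take it to 68%. This assumes removal before a response is recorded and an unchanged threshold; how often it would happen cannot be derived from the documents. Data loss and uneven handling between sites are possibilities only. The point merits correction because the toxicity is foreseeable, the cohorts are small and the remedy is short.

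**What to change.** Reconcile Table 6 (Section 5.1.5.3), Section 5.5, Section 5.5.2, Table 12 (Section 5.6.6) and Section 3.9 of the ECI guidance. Together they should give one instruction on systemic steroids for afatinib-attributed Grade 3–4 acneiform rash and one consequence for trial participation. Which rule applies is a clinical decision for the sponsor, and this review does not propose one.

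State in Section 5.5.2 that any subject removed under it enters the disease-status and adverse event follow-up already described in Sections 2.1, 5.8 and 7.4.3.

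As a minor clarification, say whether the erythromycin entry in the P-gp list covers the topical product named in Table 12.

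The cost is a few sentences in a protocol amendment, with no new procedures, visits or patients.
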